APPENDIX A **PERFORMANCE STATUS CRITERIA**

[figure not shown]
ECOG Performance Status Scale		Karnofsky Performance Scale	
Grade	Descriptions	Percent	Description
0	Normal activity. Fully active, able to carry on all pre-disease performance without restriction.	100	Normal, no complaints, no evidence of disease.
		90	Able to carry on normal activity; minor signs or symptoms of disease.
1	Symptoms, but ambulatory. Restricted in physically strenuous activity, but ambulatory and able to carry out work of a light or sedentary nature (e.g., light housework, office work).	80	Normal activity with effort; some signs or symptoms of disease.
		70	Cares for self, unable to carry on normal activity or to do active work.
2	In bed <50% of the time. Ambulatory and capable of all self-care, but unable to carry out any work activities. Up and about more than 50% of waking hours.	60	Requires occasional assistance, but is able to care for most of his/her needs.
		50	Requires considerable assistance and frequent medical care.
3	In bed >50% of the time. Capable of only limited self-care, confined to bed or chair more than 50% of waking hours.	40	Disabled, requires special care and assistance.
		30	Severely disabled, hospitalization indicated. Death not imminent.
4	100% bedridden. Completely disabled. Cannot carry on any self-care. Totally confined to bed or chair.	20	Very sick, hospitalization indicated. Death not imminent.
		10	Moribund, fatal processes progressing rapidly.
5	Dead.	0	Dead.

100
CONFIDENTIAL

[figure not shown]
This document is confidential. Do not disclose or use except as authorized.

APPENDIX B ADVERSE EVENT MANAGEMENT

Appendix B1:

[figure not shown]
Appendix B2:

102
CONFIDENTIAL

This document is confidential. Do not disclose or use except as authorized.

[figure not shown]
Appendix B3:

103
CONFIDENTIAL

This document is confidential. Do not disclose or use except as authorized.

[figure not shown]
Appendix B4:

104
CONFIDENTIAL

This document is confidential. Do not disclose or use except as authorized.

[figure not shown]
Appendix B5:

105
CONFIDENTIAL

This document is confidential. Do not disclose or use except as authorized.

[figure not shown]
Appendix B6:

[figure not shown]
106
CONFIDENTIAL

This document is confidential. Do not disclose or use except as authorized.

Appendix B7:

Appendix B8:

APPENDIX C

REGULATORY CONSIDERATIONS

Dana-Farber/Harvard Cancer Center (DF/HCC) follows the International Conference on Harmonisation Guidelines for Good Clinical Practice (ICH GCP) to the extent those guidelines reflect the regulations and guidance set forth by the Food and Drug Administration (FDA) regulations. Where the ICH GCP guidelines include recommendations or requirements that go beyond those set forth under the FDA regulations, DF/HCC may or may not choose to institute those additional recommendations or requirements.

The study will be conducted in compliance with the protocol. The protocol and any amendments and the subject informed consent will receive Institutional Review Board/Independent Ethics Committee (IRB/IEC) approval/favorable opinion prior to initiation of the study.

All potential serious breaches must be reported to the study PI, study sponsor ([name], MD PhD), and DF/HCC IRB.

A serious breach is a breach of the conditions and principles of GCP in connection with the study or the protocol, which is likely to affect, to a significant degree, the safety or physical or mental integrity of the subjects of the study or the scientific value of the study.

Personnel involved in conducting this study will be qualified by education, training, and experience to perform their respective tasks. This study will not use the services of study personnel where sanctions have been invoked or where there has been scientific misconduct or fraud (e.g., loss of medical licensure, debarment).

**DFCI Protocol #: 18-279**

**Statistical Analysis Plan**

**November 20, 2023**

**Design:** The study is an open label, phase Ib trial in which patients with stage III B/C/D or stage IV melanoma were treated with NeoVax plus Montanide® ISA-51 VG in combination with nivolumab and locally administered ipilimumab. Tumor from a surgical resection specimen or core needle biopsy of a melanoma metastasis was used to prepare DNA and RNA for sequencing. Patients began treatment with nivolumab, and vaccine was prepared during the initial 12 weeks of nivolumab therapy. At week 12, patients began vaccination with up to 20 neoantigen peptides. These peptides were encoded by non-silent mutations that were identified through DNA and RNA sequencing. Up to 20 peptides of approximately 20 amino acids in length were prepared for each patient and were administered together with the immune adjuvant poly-ICLC and Montanide® ISA-51 VG, a mineral oil-based immune adjuvant analogous to incomplete Freund's adjuvant (IFA).

Concurrently with the vaccine and nivolumab, ipilimumab was delivered via subcutaneous injection in proximity to each vaccination site to 1) direct anti-CTLA-4 activity to the vaccine-draining lymph nodes, and 2) limit systemic toxic effects. This approach has been shown to be effective in animal tumor models and was expected to result in significantly reduced levels of systemic ipilimumab compared to the approved dose/schedule in advanced melanoma (3 mg/kg q3wks for four doses in the metastatic setting). The ipilimumab dose would be escalated/de-escalated from 2.5 mg/kg flat dose per injection in Cohort 1. Serial tumor biopsies and vaccine site biopsies were performed as shown in the schema below.

The primary endpoint is the rate of DLTs (CTCAE V5.0), as outlined and defined in Section 5.5 of the protocol. We chose dose escalation cohorts of five patients, rather than a more traditional 3+3 design, because the determination of whether to treat at a different dose in this trial was made over a longer period due to the time needed for vaccine preparation and the extended period for safety evaluation. Three dosing cohorts were considered, each varying the dose of ipilimumab. The decision rule to escalate to the next dose was based on having zero or one patient (out of five) experiencing a DLT during the first 42 days of vaccine therapy. The first cohort, Cohort 1, was treated with Ipilimumab 2.5 mg per injection site.

If zero or 1 patient in Cohort 1 experienced a dose limiting toxicity (DLT) during the first 7 weeks of treatment, 5 patients would be treated as Cohort 2 (Ipilimumab 5 mg per injection site). If two or more patients in Cohort 1 experienced a DLT during the first 7 weeks of treatment, then 5 patients would be treated at Cohort -1 (Ipilimumab 1.25 mg per injection site). If none or 1 patient experienced a DLT on Cohort 2, then Ipilimumab at 5 mg per injection site would be the maximum tolerated dose (MTD) and an additional 10 patients will be treated at that dose level to increase the likelihood of detecting serious

toxicities, to complete biologic correlative endpoints, and to gain preliminary experience with clinical tumor activity. If two or more patients in Cohort 2 experienced DLT, then Dose Level 1 would be the MTD and an additional 10 patients would be treated in an expansion cohort at this dose.

If no or only 1 patient experienced a DLT on Cohort -1, then Ipilimumab 1.25 mg per injection site would be the MTD and an additional 10 patients would be treated in an expansion cohort at that dose level. If two or more patients in Cohort -1 experienced DLT, then the study will be stopped and no MTD would be declared.

The table below shows the probability of moving to the dose expansion phase (0 or 1 patients with DLT out of 5 patients at the MTD) for various possible values of the true, but unknown, toxicity rate.

True rate of DLT (%)	Probability of Dose Expansion (%)
10	92
20	74
30	53
40	34
50	19
60	9

If the true probability of DLT is 10% or less, then the probability of proceeding to dose expansion is at least 92%. The probability of dose expansion is less than 50% if the true rate of dose-limiting toxicities is 32% or greater.

**Minimum vaccination requirement to pass DLT observation period:** A minimum of 2 vaccinations and absence of DLTs are required for a patient to complete the 7-week DLT observation period successfully.

**Modified Design:** Due to slow accrual in this trial, enrollment to the expansion cohort did not begin and trial accrual was stopped at the end of the dose escalation phase, at the time the MTD was determined.

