5.5 Definition of Dose-Limiting Toxicity

Dose-limiting toxicity (DLT) is based on the CTEP Active Version (version 5.0) of the NCI Common Terminology Criteria for Adverse Events (CTCAE). DLT refers to toxicities experienced within 42 days (6 weeks of Neoantigen Vaccine treatment initiation i.e. 2 vaccinations “DLT window”). If treatment has to be delayed because of a toxicity that does not fulfill the criteria of a DLT, the DLT window should be extended by that time period of delay. A DLT will be defined as follows:

1. Grade 3 or 4 toxicity that is definitely, probably, or possibly related to the administration of vaccine, excluding:
 - Transient (\leq 72 hours) flu-like symptoms
 - Grade 3 nausea, vomiting, diarrhea, or constipation that returns to grade 2 (or lower) level within 48 hours
 - Any grade 3 rash that resolves to grade 2 or grade 1 within \leq 14 days
 - Any grade 3 endocrine abnormality that is corrected with hormonal therapy within 4 weeks
2. Grade 3 or 4 abnormal laboratory value that is definitely, probably, or possibly related to the administration of vaccine if it persists for more than 7 days, or requires hospitalization or medical intervention excluding:
 - Any grade 3 electrolyte abnormality:
 - lasts \leq 72 hours,
 - is not clinically complicated,
 - and resolves spontaneously or responds to conventional medical intervention
3. Any grade 3 or grade 4 toxicity that is considered, in the opinion of the Principal Investigator, to be dose-limiting.
4. Any death related to study treatment.

Management and dose modifications associated with the above adverse events are outlined in Section 6 (Expected Toxicities and Dosing Delays/Dose Modifications).

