6.3.2 NeoVax plus Montanide

6.3.2.1 If a participant develops grade 3 toxicity attributable to the vaccine, additional treatment will be withheld until the toxicity has resolved or improved to grade 1. If the toxicity constitutes a DLT as defined in 5.6, the participant will be removed from the study. If the toxicity does not fulfill the criteria of a DLT, the next vaccine administration may be delayed for a maximum duration of 14 days. If vaccine dosing has to be delayed more than 2 times because of an attributable toxicity that is not considered a DLT, the participant will be removed from the study

6.3.2.2 If a participant develops grade 4 toxicity attributable to the vaccine s/he will be removed from treatment

6.3.2.3 If two or more grade 4 or greater toxicities attributable to the vaccine are observed, the trial will be suspended to investigate the causes of these (unexpected) toxicities

6.3.2.4 Vaccine dosing may be delayed in the event of unrelated adverse events if it is felt to be in the medical best interest of the patient following discussion by the treating investigator with the study Principal Investigator or designee. Vaccine dosing may be resumed once the treating investigator deems it is medically safe to do so following discussion with the study Principal Investigator or designee as long as the participant has not developed progressive disease

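### The DLT window is 42 days in protocol 5.5 but 7 weeks in several decision rules; the SAP should name the 5.5 window, say which was applied, and check for events in between

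*SAP*

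**What the plan says.** **42 days or 6 weeks**
- Protocol 5.5, which defines the DLT: "DLT refers to toxicities experienced within 42 days (6 weeks of Neoantigen Vaccine treatment initiation i.e. 2 vaccinations". If treatment is delayed for a toxicity that is not itself a DLT, "the DLT window should be extended by that time period of delay".
- Protocol 5.4.3 requires two vaccinations and no DLT to complete a 6-week observation period.
- SAP, Design, decision rule: zero or one patient of five "experiencing a DLT during the first 42 days of vaccine therapy".

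**7 weeks**
- Protocol 5.4.1 and 13.1, Cohort 1 rules.
- Protocol 13.1, the observation-period sentence and the expansion-cohort stopping rule.
- SAP, Design, Cohort 1 rule: zero or one patient who "experienced a dose limiting toxicity (DLT) during the first 7 weeks of treatment".
- SAP, Design, observation period: "A minimum of 2 vaccinations and absence of DLTs are required for a patient to complete the 7-week DLT observation period successfully".

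**Cross-references**
- Protocol 5.4.1 and 13.1 both send the reader to 5.5 for the DLT assessment time.
- The SAP sets its primary endpoint "as outlined and defined in Section 5.5 of the protocol".

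**Analysis and status**
- The SAP's primary analysis (Statistical Analyses, Primary Endpoints) gives the proportion of patients with a DLT and repeats no window. Its toxicity variables include a DLT flag, D_toxdlt, with no note of the window used to set it.
- The SAP's Modified Design paragraph says that "trial accrual was stopped at the end of the dose escalation phase, at the time the MTD was determined".

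**The concern.** The DLT rate is the primary endpoint, and its time window is part of its definition. The SAP gives two windows in adjoining paragraphs. Nearly the same sentence on completing the observation period says 6 weeks in protocol 5.4.3 and 7 weeks in protocol 13.1 and the SAP.

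The extra week is not a quiet one. Doses are scheduled at weeks 12, 15, 18 and 21, so dose 3 is nominally due on day 42. Section 5.5 describes its window as covering two vaccinations, whereas the 7-week wording also takes in the days after a third dose of vaccine and local ipilimumab.

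The cohort call turns on one patient: 1 of 5 escalates and 2 of 5 does not. The expansion cohort was never opened, so the small escalation cohorts are the whole basis for the reported DLT rate.

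**Working it through.** **1. The plan's own table.** Inputs are five patients per cohort and a pass at 0 or 1 DLT (protocol 13.1; SAP, Design). The formula is P(pass) = (1−p)^5 + 5p(1−p)^4.

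At p = 10/20/30/40/50/60% this gives 91.9/73.7/52.8/33.7/18.8/8.7%, against the stated 92/74/53/34/19/9%. The table reproduces. Its rates carry no time window, so it stays correct if they are read as 42-day rates.

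**2. The gap between the windows.** 7 weeks = 7 × 7 = 49 days, so the wordings differ by 49 − 42 = 7 days. Dose 3 is due (18 − 12) × 7 = 42 days after dose 1. With no delay, the 42-day window lies wholly inside the 49-day window and the difference is days 43 to 49.

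**3. What an extra week could do.** No document gives a hazard. Two assumptions are used to show a range:
- (a) Constant daily hazard: p49 = 1 − (1 − p42)^(49/42).
- (b) Risk follows doses, with equal risk per dose, two doses in 42 days and three in 49: p49 = 1 − (1 − p42)^(3/2). This puts all of dose 3's risk in the extra week.

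Because the windows are nested when there is no delay, the chance of a different cohort call is P(pass at 42 days) − P(pass at 49 days).

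| 42-day risk | P(pass), 42 d | (a) p49 | (a) P(pass) | (a) gap, points | (b) p49 | (b) P(pass) | (b) gap, points |
|---|---|---|---|---|---|---|---|
| 10% | 91.9% | 11.6% | 89.5% | 2.4 | 14.6% | 84.2% | 7.6 |
| 20% | 73.7% | 22.9% | 67.7% | 6.1 | 28.4% | 56.0% | 17.7 |
| 30% | 52.8% | 34.0% | 44.7% | 8.1 | 41.4% | 31.3% | 21.6 |

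Gaps are taken before rounding. For example, at 20% under (a), 0.7373 − 0.6766 = 0.061.

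**4. Which window governs.** Section 5.5 makes the time limit part of what a DLT is. Protocol 5.4.1 and 13.1 defer to 5.5 for the assessment time, and the SAP defers to it for the endpoint. No text sends the reader the other way, to 7 weeks.

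**The case against.** The strongest reply is that there is little to resolve. If a DLT is by definition an event within the 5.5 window, then a toxicity on day 45 in an undelayed patient is not a DLT. A rule counting DLTs over 7 weeks then gives the same count as one counting over 42 days. On that view D_toxdlt inherits the 5.5 window, and only a labelling slip remains.

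The first part stands: 5.5 governs, and a reader who infers that the documents give no guidance goes too far. It does not settle what was done. The 7-week observation period is stated outright and contradicts 5.4.3. The SAP describes the decisions in retrospect under both windows and does not say which one was used to classify events.

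Three stronger readings are tempting and are not supported:

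- *The declared MTD is in doubt.* The rules for Cohort 2 and for the lower dose level state no 7-week window. The MTD is reached only if the general 7-week observation sentence was applied there, which no document says.
- *After a delay the 5.5 window becomes the longer one.* For a non-DLT grade 3 vaccine toxicity, protocol 6.3.2.1 says "the next vaccine administration may be delayed for a maximum duration of 14 days", so the 5.5 window could run to 42 + 14 = day 56. But passing the 7-week mark requires 7 weeks to be a fixed 49 days. Protocol 5 and 5.2.2.2 hold the day count during a toxicity hold. If that applies here, 7 weeks becomes 49 + 14 = 63 days and the windows stay nested. No text ties the held count to the DLT window either way.
- *The chance of a different call is a known 2 to 8%.* That range comes from one assumed hazard. Nor does 14 days cap the total delay: 6.3.2.1 removes a patient only after more than two delays, and 6.4 allows holds of up to 6 weeks.

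It is also fair that no dosing decision can now change.

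**Conclusion.** The inconsistency is real and concerns the primary endpoint. Section 5.5 governs, and the 7-week statements in protocol 5.4.1, protocol 13.1 and the SAP are the ones in error. One otherwise qualifying event on days 43 to 49 in an undelayed patient could turn a 1-of-5 result into 2 of 5 and change the Cohort 1 call. The documents do not show whether such an event occurred, and nothing in them says that a decision was wrong.

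The size is illustrative only: roughly 2 to 22 points per cohort across the two hazard assumptions and 42-day risks of 10 to 30%, with no delays. The published probability tables are unaffected. What remains open is the reported DLT rate and whether any conclusion depends on the window.

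**What to change.** 1. In the SAP's primary analysis, state that the DLT rate uses the protocol 5.5 window: 42 days from first vaccination plus its delay extension.
2. Correct or annotate the 7-week wording in the SAP's Design section, stating which window was actually applied to the cohort decisions and to D_toxdlt. Do not simply overwrite it: the text describes decisions already taken, and a silent change could misreport conduct.
3. Add the adverse-event onset date to the analysis variables; the SAP's toxicity list has a timing flag but no onset date. Using it with the first-vaccination date, report any otherwise DLT-qualifying event that falls in one window but not the other, in either direction. If there is none, one sentence says so.
4. State whether the DLT count at each dose level, or the declared MTD, depends on the window.
5. Record that 5.5 supersedes protocol 5.4.1 and 13.1 on this point, so that the SAP and protocol agree.

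The cost is a few sentences, one added variable and a check by date in cohorts planned at five patients each. Dosing and enrolment do not change.

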## Endpoints

**1. Primary Endpoint:** The primary endpoint was safety and toxicity, specifically the rate of DLT. Adverse events to assess the safety and side-effect profile of the NeoVax were recorded using Common Terminology Criteria for Adverse Events (CTCAE) version 5.0.

### 2. Secondary Endpoints

- a. Objective antitumor response: Best overall response (complete response (CR) or partial response (PR)) per RECIST 1.1.
- b. Disease progression/recurrence: The number of patients with disease progression among those with unresectable disease, or disease recurrence in those with resectable disease.

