1.3 Secondary Objective

- To assess the induction of neoantigen-specific cellular immune responses following administration of NeoVax plus Montanide in combination with Nivolumab and locally administered Ipilimumab
- To estimate rates of disease progression/recurrence depending on whether the patient had all melanoma resected or has measurable disease per RECIST 1.1

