Timelines: We expect to enroll one patient per month. We expect FPFV to occur by September 2020. LPFV is expected for July 2022 and overall duration of the study will be 4 years.

Analysis of Secondary Endpoints

Secondary endpoint in this clinical trial will: (a) assess the induction of IFN- γ T-cell response or tetramer staining to the assay peptides, and (b) to estimate rates of disease progression or recurrence (RECIST 1.1) depending on whether the patient is resected or has measurable disease. Analyses of the secondary endpoint will be based on 15 patients treated at the MTD.

The induction of IFN- γ T-cell response will be based on ELISPOT assessments taken prior to vaccine administration and at week 16. The proportion of patients who achieve more than 55 SFU/10⁶ PBMC or 3 times their baseline level will be presented with a 90% exact binomial

confidence interval. Based on a cohort of size 15, the confidence interval will be no wider than 0.46.

The proportions of patients with disease progression or recurrence, according to melanoma stage, will be presented with 90% exact binomial confidence intervals.

Analysis of Correlative Endpoints

Longitudinal analyses of PBMC immune response kinetics to the peptide pool and to individual epitopes will be presented graphically and descriptively at each time point. Changes in the magnitude of the response relative to pre-treatment at several different time points after vaccination will be summarized descriptively. Changes in response between pre-treatment and 16 weeks post-vaccination, which is the time of the primary immunologic endpoint, will be assessed using the Wilcoxon signed-rank test.

Immune studies of T cell subpopulations (CD4⁺, CD8⁺, central/effector memory cells, Th1/Th2 cells, T-reg, etc.), myeloid-derived suppressor cells (MDSC), CTL response, and T cell activation status will be summarized using descriptive statistics.

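### The SAP, written after accrual ended, gives objective response a secondary-endpoint status that the protocol's two lists do not give it, and does not label the change

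*SAP*

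**What the plan says.** Protocol Section 1.3 has two secondary objectives. The first begins "To assess the induction of neoantigen-specific cellular immune responses following administration of NeoVax plus Montanide". The second reads "To estimate rates of disease progression/recurrence depending on whether the patient had all melanoma resected or has measurable disease per RECIST 1.1". Section 13.1 repeats the pair as endpoints: IFN-γ T-cell response or tetramer staining, and "to estimate rates of disease progression or recurrence (RECIST 1.1) depending on whether the patient is resected or has measurable disease".

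The SAP, under Endpoints, 2. Secondary Endpoints, lists (a) "Objective antitumor response: Best overall response (complete response (CR) or partial response (PR)) per RECIST 1.1" and (b) "Disease progression/recurrence: The number of patients with disease progression among those with unresectable disease", with recurrence counted in resectable disease. Its Statistical Analyses section repeats these two items and divides the response count by the number of patients in each cohort.

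The SAP is dated "November 20, 2023". It opens with "The study is an open label, phase Ib trial" and states under Modified Design that "trial accrual was stopped at the end of the dose escalation phase, at the time the MTD was determined".

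**The concern.** An endpoint list completed after accrual in an open-label trial can present an outcome as planned when its rank was settled late. A reader of the results would take a CR/PR rate by cohort to be one of the trial's pre-specified secondary results, because the SAP text reviewed does not say that the protocol lists it nowhere as secondary. The same reader would not learn that the protocol's first secondary endpoint, immune response, is missing from the SAP's list.

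The label matters more because response is hard to attribute here. Protocol Section 11.1.4.4 counts best response from the start of treatment, and treatment starts with about 12 weeks of nivolumab alone, so a response to nivolumab before any vaccine would count.

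**Working it through.** The documents size nothing on objective response, so the check is mainly a comparison of lists, dates and definitions.

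**1. The lists side by side**

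| Item | Protocol 1.3 | Protocol 13.1 | SAP endpoint list | SAP secondary analyses |
|---|---|---|---|---|
| Immune response | listed | listed; proportion with 90% exact interval | not in text reviewed | not in text reviewed |
| Progression/recurrence | listed | listed; proportion with 90% exact interval | listed (b) | listed (b) |
| Objective response | not listed | not listed; no analysis given | listed (a) | listed (a); rate per cohort |

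**2. What could have been known.** Vaccination starts at week 12. The DLT window is 6 weeks in Protocol 5.5 and 7 weeks in 13.1, so a patient who completes it has reached week 12 + 6 = 18 or 12 + 7 = 19. Protocol 5.7 refers to a week 12 scan. Patients who completed the window and counted towards the MTD decision were therefore due at least one on-treatment scan before that decision, and the SAP was written after it. This shows that response data could have been available. It does not show that they were used.

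**3. What the protocol fixed in advance**
- the set evaluable for tumor response: unresectable, measurable disease and at least one vaccine dose (5.4.3), with a further definition requiring re-evaluation (11.1.1)
- assessment by standard criteria, with response said only not to be primary (opening of Section 11)
- RECIST 1.1 criteria for CR and PR (11.1.4)
- best overall response, with tables (11.1.4.4)

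The new elements are the secondary status and the denominator.

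**4. The denominator.** With r responders among m measurable patients in a cohort of n, the SAP gives r/n and Protocol 5.4.3 gives r/m. The escalation design gives n = 5. The documents do not give m, so it is an assumption:
- m = 5: r = 1 gives 1/5 = 20% both ways
- m = 3: r = 1 gives 1/5 = 20% against 1/3 = 33%
- m = 3: r = 2 gives 2/5 = 40% against 2/3 = 67%

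When all responders are in the measurable set, the SAP rate is equal to or below the protocol rate.

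**5. Precision, for context.** Section 13.1 states that a 90% exact binomial interval on 15 patients is no wider than 0.46. The limits are the 5% quantile of Beta(x, n−x+1) and the 95% quantile of Beta(x+1, n−x). The largest width at n = 15 is 0.456 (x = 8), which agrees. The expansion cohort never opened. For a cohort of 5 the largest width is 0.734 (x = 3).

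**The case against.** The strongest defence is that response was planned. The protocol sets out who is evaluable, how response is measured and confirmed, and how best overall response is derived. Sections 5.4.1 and 13.1 also give preliminary experience of tumor activity as a purpose of the expansion cohort. This stands in part: a note saying only that CR/PR was added in the SAP would wrongly imply that the measure was invented then. It does not give response secondary status, because both formal lists omit it and Section 13 has no analysis for it.

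A second defence is that the SAP's analysis is already descriptive, with no test, threshold or comparator, so being listed first has no inferential consequence. That also stands. What remains is how the result is described to readers.

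A third is that part of the SAP following the endpoint list was not available to this review. The absence of a label, and of the immune-response endpoint, is therefore asserted only for the text seen. The SAP's secondary analysis section was seen and has neither.

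A reader might also turn to the nivolumab-alone response rate in Protocol 2.3.5.4 (33/107 = 31%). If all 5 patients in a cohort were measurable and the vaccine and local ipilimumab added nothing, the chance of at least one responder would be 1 − 0.69^5 = 84%. The arithmetic is right, but the figure would be the same had response been listed from the start. It describes a small uncontrolled cohort, is not evidence of late selection, and assumes a number of measurable patients that the documents do not give.

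**Conclusion.** The concern holds as a matter of status and labelling. After accrual ended in an open-label trial, the SAP gave CR/PR a secondary rank found in neither protocol list, without saying so in the text reviewed. The same text omits the protocol's immune-response endpoint and uses a response denominator different from Protocol 5.4.3.

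A reader might infer that response was chosen because responses had been seen. The documents do not support that: no section says who set the list, when, or with what data in view. The denominator also tends to lower the rate, which does not suggest a search for a favourable figure.

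No planned calculation is wrong. The consequence is that an outcome may be read as a pre-specified secondary result when only its measurement was pre-specified. The conclusion rests on the SAP date, its statement on accrual, and the assumption that the unseen SAP text carries no explanation. The size of the denominator effect depends on the unknown number of measurable patients.

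**What to change.** In the SAP's endpoint list and secondary analysis section:

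1. Keep the protocol's two secondary endpoints. Restore immune response with its analysis, or state that it is removed and why.
2. Report CR/PR descriptively under a label such as: *assessed per protocol Section 11; not a listed secondary endpoint in protocol 1.3 or 13.1; secondary status assigned after accrual ended*. Carry the label into the results tables and the publication.
3. Reconcile the response denominator with Protocol 5.4.3 and 11.1.1. Either use the response-evaluable set or give both rates, with the number of measurable patients in each cohort.

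The first step means writing up an analysis that Protocol 13.1 already describes; the others are wording and one extra count per cohort. The small downside is that the response rate carries less weight in the report.
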